### I. Background and Significance:

**Retention in medication treatment for opioid use disorder (OUD) decreases overdose mortality:** Medication treatment for OUD with buprenorphine, methadone, or extended-release naltrexone reduces the risk for overdose by 70%. As such, the current director of National Institute on Drug Abuse (NIDA) cites the increase in access to medications for OUD as one of the four central aims in reversing the opioid crisis. However, treatment dropout rates remain unacceptably high—approximately 50% of patients will have discontinued treatment 6 months after initiation. Therefore, there is a critical need to ensure patients not only have access to medications, but also are retained in treatment longer.

**Cravings play a central role in OUD relapse and treatment discontinuation:** There is a substantial body of research indicating that high rates of treatment discontinuation are due to the emergence of intense cravings to use illicit opioids in response to cues—which are reminders of the drug such as drug paraphernalia. The brains of individuals with OUD are highly susceptible to experiencing strong cravings in response to environmental cues, and strength of the cravings correlates positively with the severity of the illness. Even among individuals with OUD who have been abstinent for over a year, strong cravings can be elicited in response to cues. Therefore, much of the research so far in improving treatment retention on medications for OUD have focused on helping patients learn how to avoid triggers and to manage their cravings if they do emerge.

**Psychosocial treatments as adjuncts to medications have not been as helpful as hoped:** Interventions such as *cognitive-behavioral therapy* and *relapse prevention* teach skills to reduce exposure to cues and to learn how to manage cravings. Unfortunately, in numerous randomized clinical trials among patients with OUD on buprenorphine, these treatments were less effective than one would hope for in improving treatment retention or suppressing the use of illicit opioids. As such, there is a critical need to identify novel strategies that will improve retention in medication treatment for OUD.

**Cannabidiol (CBD) has emerged as a possible adjunct to OUD treatment:** CBD is a non-psychoactive and non-addictive constituent in marijuana. Both animal and human studies have identified that CBD possesses antiepileptic, anxiolytic, antipsychotic and other therapeutic properties, while producing minimal if any adverse effects. While the mechanisms of action are being elucidated, CBD is an inverse agonist at the cannabinoid receptors and appear to target brain regions that mediate cue-induced cravings. CB1 and CB2 receptors are densely located in striatal regions that mediate reward function, and also modulates serotonin and opioid receptors. Cannabinoid receptors also modulate nociception, inhibit pro-inflammatory molecules, and display synergism with systems that influence analgesia such as the endogenous opioid system. In animals, CBD administration blocks the reward-facilitating effects of morphine, reduces opioid withdrawal symptoms, and attenuates cue-induced relapse among abstinent

rats. In 2018, CBD was approved by the FDA for the treatment of pediatric seizures, and reclassified as a Schedule V drug, opening up the path for human trials.

**CBD reduces cue-induced cravings for individuals with OUD who are not taking any medications:** To date, there are two double-blind, placebo-controlled randomized trials for CBD for OUD which have been published, but only among abstinent individuals not taking medications. In both studies, either CBD (400mg or 800mg) or placebo were administered for 3 days, and the increase in cravings in response to heroin-related cues was measured. Results showed greater reduction in cue-induced cravings among those taking CBD compared to placebo, with minimal adverse effects. This adds to the growing body of data suggesting the relevance of CBD in modulating the attentional saliency of drug related cues which contribute to the risk for relapse.

**Impact of CBD on cue-induced cravings among individuals stabilized on buprenorphine is not known:** A prior study of individuals with OUD who are receiving buprenorphine for detoxification (i.e. several days of tapering dose of buprenorphine) noted that participants remained highly reactive to cues. Results from patients on long-term methadone treatment implies that cue-reactivity may decrease over time. Given that long-term medication treatment remains the gold-standard approach, a critical question that remains unanswered is whether CBD can be used as an adjunct to buprenorphine treatment to reduce cue-induced cravings. If promising, the preliminary data will be used to seek NIDA R01 or R21 funding to conduct a placebo-controlled, double-blind, randomized clinical trial to examine the impact of CBD on cue-induced cravings among individuals with OUD taking medications. Longer-term, our goal is to examine the impact of CBD on treatment retention for OUD as an adjunct to medications in trials of longer duration. We will study the effectiveness of this approach with specific medical and psychiatric populations with OUD. If successful, this line of research has the potential to significantly impact clinical practice of treating OUD by providing a viable medication adjunct to existing evidenced-based therapies.

**Individual differences in pain processing and central sensitization:** Psychophysics, which is the careful and systematic testing of sensory processing in humans in a laboratory setting, with standardized equipment and protocols, has revealed important differences amongst individuals taking opioid analgesics, including higher pain sensitivity. Specifically, central sensitization is a process by which the spinal nociceptive system responds to sustained noxious peripheral input by amplifying the transmission of this signal, and has proven to be an important mechanism in the development of chronic pain in preclinical research. A clinical correlate of central sensitization is temporal summation of repetitive painful stimuli. Importantly, variability in temporal summation, measured by the increase in pain sensation during a sequence of stimuli, is observed among individuals and groups and may indicate an individual's endogenous analgesic response. Temporal summation has been shown to distinguish differences between low- and high- opioid users, and risk for opioid misuse. By including a quantitative sensory testing (QST) assessment of both pressure pain threshold/tolerance and temporal summation of pain (TSP) in this study, we will gain valuable pilot data on: (1) how much patients with OUD on buprenorphine exhibit central sensitization, and how they may differ from chronic pain patients and healthy volunteers (from our other studies); and (2) how CBD impacts central sensitization, by performing a pair-wise comparison of temporal summation of pain of patients before and after they begin taking CBD.

## **II. Specific Aims:**

**Study Aim:**

To determine the impact of CBD on cue-induced cravings among individuals with OUD on buprenorphine or methadone treatment.

- In a single-arm, open-label study, subjects will receive 600mg of oral CBD once daily for 3 consecutive days. Cue-induced cravings will be assessed before and after the intervention. We hypothesize that cue-induced cravings after CBD administration will be reduced by 50% compared to cue-induced cravings prior to the intervention.

**III. Subject Selection:**

The proposed study is a single-arm, open-label feasibility pilot. The study will enroll 12 adult subjects (including 2 pilot subjects) with OUD currently receiving treatment with buprenorphine or methadone.

**Inclusion criteria:**

- Diagnosis of DSM-5 opioid use disorder, severe
- Currently in treatment with methadone or buprenorphine

**Exclusion criteria:**

- Requiring level of care higher than outpatient treatment for alcohol, sedative/hypnotics, or stimulants
- Any current mood episode requiring level of care higher than outpatient treatment
- History of psychotic disorder
- Currently pregnant
- Hepatic liver enzymes greater than 3x upper normal limit
- Hypersensitivity to cannabinoids or sesame oil (CBD solution comes in sesame oil emulsion)
- Currently taking any medications with known significant pharmacokinetic interactions with CBD

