**Schedule of visits and assessments:**

The blood and urine samples (see **Table**

**1**) collected during the Baseline Visit 1 and Post-Exposure Visit 3 will be used only for inclusion/exclusion purposes.

Specifically, participants who are currently pregnant (as confirmed by the pregnancy test), have hepatic liver enzymes greater than three times the upper normal limit (as confirmed by the liver

function tests, or LFTs), or who are not taking their buprenorphine as clinically prescribed (as confirmed by the urine toxicology) will be excluded. Other inclusion/exclusion criteria not dependent on blood and urine samples are detailed elsewhere in this protocol. Baseline measures and the pre-exposure cue-induced cravings, anxiety, and pain assessments will both be conducted before the CBD administration. The first oral CBD administration will occur during Visit 2, following the pre-exposure assessment. Participants will be instructed to take the second and third oral CBD doses at home, and will be asked to complete a drug diary which will also assess general craving and adverse effects. Participants will be asked to take their regular dose of sublingual buprenorphine at their regular time, and to return to the BWH Center for Clinical Investigation for Visit 3 following their last home administration of oral CBD. Follow-up assessments, including post-exposure cue-induced cravings, anxiety, and pain assessments, will occur after administration of CBD. During Visits 2 and 3, general craving, anxiety, and pain scales will also be administered before the cue-reactivity paradigm. There will also be continuous physiological monitoring (vital signs: heart rate, blood pressure, respiration rate, oxygen saturation, and temperature) during Visits 2 and 3. Table 1 summarizes the schedule of visits and assessments.

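### Eligibility does not address current use of CBD products or cannabis, so for any user the Visit 2 pre-exposure test may not be CBD-free, and no analysis would show it

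*Combined protocol and SAP*

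**What the plan says.** **Eligibility (Section III).** Besides the opioid use disorder diagnosis, the only inclusion criterion is "Currently in treatment with methadone or buprenorphine". The substance exclusion, "Requiring level of care higher than outpatient treatment for alcohol, sedative/hypnotics, or stimulants", covers three drug classes and works through level of care rather than use. Two other exclusions come near the subject. One is hypersensitivity to cannabinoids. The other is "Currently taking any medications with known significant pharmacokinetic interactions with CBD", which concerns drugs that interact with CBD, not CBD or cannabis. Section IV, the study procedures, and the rule under Potential difficulties limiting time in treatment to between one month and one year add nothing on cannabinoids.

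**Data already planned (Section V).** Blood and urine are collected at Visits 1 and 3 and serve eligibility only. The one toxicology-based exclusion is of participants "who are not taking their buprenorphine as clinically prescribed (as confirmed by the urine toxicology) will be excluded". The Timeline Followback is listed in Table 1 with no substances, look-back period or use stated. The home drug diary is described as covering the doses, general craving and adverse effects.

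**The contrast.** Section I states that "CBD is a non-psychoactive and non-addictive constituent in marijuana" and describes the pain objective as a "pair-wise comparison of temporal summation of pain of patients before and after they begin taking CBD". Section V labels the Visit 2 tests, done before the first study dose, as pre-exposure. Section VI makes the within-subject change from that test to Visit 3 the primary outcome. There is no control arm.

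**The concern.** With a single arm, the Visit 2 measurement is the only comparator. If a subject has been taking a CBD product, or cannabis containing CBD, up to Visit 2, that measurement may already carry some of the effect under study. If the subject starts, stops or changes such use between Visits 2 and 3, the resulting shift in craving, anxiety or pain enters the change score and is read as an effect of study CBD.

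What is at stake is mainly the estimate. Section VI gives the primary interest as effect sizes and variance for planning a larger randomised trial. Mixing users and non-users could distort both, and with 10 subjects two or three users are enough to matter. Section IV says the criteria are meant to favour internal validity and a homogeneous group; for the compound under study the list does not do that. Because no rule links the collected data to cannabinoid use, the plan as written would not reveal the problem afterwards.

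**Working it through.** **1. Is there a bar anywhere?** The inclusion and exclusion lists, Section IV, the visit procedures and Potential difficulties were read for three things: an exclusion for use, a cannabinoid-free period, and an instruction about use between visits. None contains any of these. Nor does any section attach an eligibility or analysis consequence to a cannabinoid finding on the toxicology, Timeline Followback or diary.

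**2. The plan's own power figure.** Inputs from Section VI: mean change -1.5, SD 1.5, r = 0.60, n = 10, two-sided alpha 0.05, paired t-test. Reading 1.5 as the per-visit SD:

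- SD of change = 1.5 × √(2 × (1 - 0.60)) = 1.342
- Standardised change = 1.5 / 1.342 = 1.118
- Noncentral-t power at n = 10: 0.881, which agrees with the stated 88%.

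**3. Illustration of dilution.** The documents give no prevalence of cannabis or CBD-product use and no degree of attenuation. Both are assumptions here. Suppose k of 10 subjects are users whose mean change is half that of the rest (-0.75), with the same within-group SD of 1.342. The pooled SD is √(1.342² + f(1 - f) × 0.75²), with f = k/10.

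| Users (k of 10) | Mean change | Pooled SD of change | Standardised change | Power, n = 10 |
|---|---|---|---|---|
| 0 | -1.50 | 1.342 | 1.118 | 88% |
| 2 | (8 × -1.5 + 2 × -0.75)/10 = -1.35 | 1.375 | 0.98 | 79% |
| 3 | (7 × -1.5 + 3 × -0.75)/10 = -1.275 | 1.385 | 0.92 | 74% |

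The powers are simulated with exactly k users; the noncentral-t approximation gives 79% and 74% as well. If users showed no change at all, simulated power would be about 64% (k = 2) or 49% (k = 3). That is an extreme bound, discussed under the objection.

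**4. The cost of excluding users instead.** If users are removed and not replaced, with the standardised change back at 1.118:

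- n = 8: power 77%, against 79% if the two users stay at half contrast
- n = 7: power 69%, against 74% if the three users stay at half contrast

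Potential difficulties expects 25 to 30 screened per month for 8 months with at least 5% enrolled. That is 25 × 8 × 0.05 = 10 at the low end and 30 × 8 × 0.05 = 12 at the high end, against a target of 10. The low end leaves no slack, although 5% is a stated minimum.

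**The case against.** The strongest reply is that the stated aim (Section II) compares cravings before and after the study intervention, not a CBD-naive state with a CBD-exposed one. In a paired design, steady background use is present at both visits, so the change still estimates the effect of adding study CBD. This stands. A reader might infer that the trial as a whole fails to measure the effect of starting CBD. The documents do not support that: the problem is confined to subjects who use these products, and only the pain-testing text in Section I speaks of patients beginning CBD.

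A reader might also take the no-change figures (64% and 49%) as the expected loss. They require background use to produce already the full effect of the 600 mg study dose, and nothing in the documents supports that. Nor is bias towards zero assured, because a change in use between visits could push the result either way.

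It can fairly be added that this is a feasibility pilot in which habituation, expectancy and time are also uncontrolled, and that excluding every cannabis user could cost more power than it saves (step 4). That argues against a blanket exclusion as the default. With replacement of those excluded, or near-zero contrast in users, exclusion would do better; the documents do not settle which applies.

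Finally, the toxicology cannot be assumed to verify abstinence at Visit 2. Section V places urine collection at Visits 1 and 3, and no section says the panel detects cannabinoids. None of these replies explains why use of the study compound itself is neither barred nor recorded.

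**Conclusion.** The omission is established by the text: current use of CBD products or cannabis is neither excluded nor tied to any planned measurement or analysis. For users, the Visit 2 baseline may not be CBD-free, and a change in use before Visit 3 may be mistaken for a treatment effect. Dilution is the more probable result, but the direction is uncertain and the size cannot be derived from the documents. The figures of 79% and 74% rest on assumed use in 2 or 3 of 10 subjects and an assumed halving of their change; they illustrate sensitivity and do not challenge the stated 88%, which reproduces. The point merits a cheap correction because the effect size and variance are what the pilot is meant to supply to the next trial.

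**What to change.** - **Eligibility (Section III, exclusion criteria).** Exclude current use of non-study CBD products within a window before Visit 2, its length set by the sponsor, assessed by self-report on the Timeline Followback. State the substances and look-back period it covers.
- **Recording (Section V).** Record cannabis and CBD-product use at Visit 2 and, in the existing drug diary, through Visit 3.
- **Analysis (Section VI).** Report the primary change and its 95% confidence interval for all subjects and again without those reporting such use.
- **Left to the sponsor.** Decide whether to exclude all cannabis users, weighing a cleaner contrast against enrolment. Use the Visit 1 and Visit 3 toxicology as a check only if the panel covers cannabinoids.

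Cost: one eligibility line, an item at Visit 2 and in the diary, and one extra analysis. A few screened patients would be lost, and the non-user analysis would have a smaller n and a wider interval. Self-report is imperfect, but it needs no new sample or assay.

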**IV. Subject enrollment:**

Adults with a DSM-5 diagnosis of OUD and who are currently in treatment with buprenorphine or methadone will be recruited. Inclusion and exclusion criteria are listed above, which are designed to favor internal validity given the preliminary nature of this trial, and to recruit as homogenous of a group of subjects as possible. Patients with OUD at Brigham and Women's Hospital (BWH) and Brigham and Women's Faulkner (BWF) Addiction Recovery Program (ARP) will be recruited via Patient Gateway for possible inclusion. Subjects will also be recruited from the Partners Clinical Trials website, <http://Rally.partners.org>, as well as print advertisements and flyers, which will also be distributed to local methadone and buprenorphine clinics. Subjects will also be recruited via automated IRB-approved recruitment emails sent from their providers at BWH Bridge and/or BWFH ARP through the "Patient Gateway Blast." All study visits will be conducted at the BWH Center for Clinical Investigation. Study staff will perform a preliminary screen to establish suitability for the study. If suitable, a study staff will obtain informed consent and apply the inclusion and exclusion criteria. If the subject meets the full inclusion and exclusion criteria, the subject will be enrolled. Subjects will not be enrolled from among the Investigator's own patients as the Principal Investigator is no longer seeing any patients clinically.

**V. Study procedures:**

**Overall approach:** After obtaining informed consent, participants will complete the baseline assessments as outlined in **Table 1**. The subject will then be scheduled for their study visits 2 and 3.

**Schedule of visits and assessments:**

The blood and urine samples (see **Table**

**1**) collected during the Baseline Visit 1 and Post-Exposure Visit 3 will be used only for inclusion/exclusion purposes.

Specifically, participants who are currently pregnant (as confirmed by the pregnancy test), have hepatic liver enzymes greater than three times the upper normal limit (as confirmed by the liver

function tests, or LFTs), or who are not taking their buprenorphine as clinically prescribed (as confirmed by the urine toxicology) will be excluded. Other inclusion/exclusion criteria not dependent on blood and urine samples are detailed elsewhere in this protocol. Baseline measures and the pre-exposure cue-induced cravings, anxiety, and pain assessments will both be conducted before the CBD administration. The first oral CBD administration will occur during Visit 2, following the pre-exposure assessment. Participants will be instructed to take the second and third oral CBD doses at home, and will be asked to complete a drug diary which will also assess general craving and adverse effects. Participants will be asked to take their regular dose of sublingual buprenorphine at their regular time, and to return to the BWH Center for Clinical Investigation for Visit 3 following their last home administration of oral CBD. Follow-up assessments, including post-exposure cue-induced cravings, anxiety, and pain assessments, will occur after administration of CBD. During Visits 2 and 3, general craving, anxiety, and pain scales will also be administered before the cue-reactivity paradigm. There will also be continuous physiological monitoring (vital signs: heart rate, blood pressure, respiration rate, oxygen saturation, and temperature) during Visits 2 and 3. Table 1 summarizes the schedule of visits and assessments.

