## VI. Biostatistical analysis:

Our primary interest in this pilot study is in estimating the effect sizes and variance in the outcomes to inform the design of a larger randomized trial. We will calculate the effect size representing the magnitude of change over time in the cue-reactivity score, defined as the difference in scores between heroin-related and neutral cues. The primary outcome is the change in cue-induced craving from pre-exposure to post-exposure. If the change in cravings is normally distributed, then a paired-samples t-test will be used to examine the statistical significance of the change in cue-induced craving. Accounting for the possibility of reduced cue-reactivity for participants taking buprenorphine compared to those not taking any medications, the estimated mean change in cue-induced cravings scores from prior studies is -1.5 (SD 1.5). Based on this estimate, and a conservative estimate of a correlation of  $r=0.60$  between the two time points, a sample size of 10 is needed for 88% power and two-tailed alpha set at 0.05 for a paired-samples t-test. A point estimate of the difference in the change and the 95% confidence interval will be reported. Conversely, if the change in cravings is not normally distributed, then a sum rank test will be used.

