the degree of distress to be very limited. All research personnel will be extensively trained on study procedures, including the conduct of the interviews that elicit personal information, and the importance of being sensitive to and respectful of all participants. In cases where emotional distress does occur, research personnel will be trained on how to identify and address it, and when to terminate an interview. Multiple levels of back-up support for research personnel will be developed. The candidate is a board certified psychiatrist, and will be able to ensure that appropriate services are received.

**Adverse reactions to cue-exposure:** The cue exposure procedure will end with a standardized relaxation and debriefing exercise. Before participants are discharged from each study session, their well-being will be assessed by the study staff and a standardized safety and adverse events questionnaire will be used to assess any adverse events. If needed, participants will be referred for further clinical evaluation and assistance. It is important to note that cue-exposure is a safe paradigm for studying craving in this population when employing debriefing procedures.

**Suicidal ideation:** Patients with OUD frequently have psychiatric co-morbidities, namely depression. Participants who disclose any suicidal ideation during the study (either through spontaneous expression of suicidal ideation, or self-reported on the M.I.N.I. screen or the PHQ-9) will result in emergent evaluation by a licensed clinician member of the study staff for appropriate assessment and triage. Any disclosures will be handled within existing legal mandates, clinical practice, and social norms. Consistent with standard clinical practice, when possible, disclosures will be discussed with the participant to determine the best management options. This may include notifying the outpatient providers or family members, referring to medical treatment, calling emergency services, or escorting the participant to the Emergency Room at Brigham and Women's Hospital. When required by law, the police department will be notified. The candidate is a board certified psychiatrist and has extensive experience managing acutely distressed patients with mental or substance use disorders.

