**Cannabidiol medication safety:** All subjects in this pilot trial will receive 600mg of cannabidiol for 3 consecutive days. Cannabidiol (Epidiolex) is approved by the U.S. Food and Drug Administration (FDA) for the treatment of seizures associated with two rare and severe forms of epilepsy. However, cannabidiol is not approved by the FDA for treatment of opioid use disorder. This protocol has been reviewed by the Center for Drug Evaluation and Research at the Food and Drug Administration to determine whether it meets the regulatory criteria for an exemption from the requirement for the submission, and we received the FDA IND exemption letter November 13, 2019. Although this proposed clinical evaluation is for an "off-label" indication of cannabidiol, it does not involve a route of administration or dosage level or use in a patient population or other factor that significantly increases the risks (or decreases the acceptability of the risks) associated with the use of the Epidiolex (cannabidiol). The proposed dose is within FDA-approved mg/kg maximum daily dose limits. There are now two randomized placebo-controlled studies of administering 400mg or 800mg of cannabidiol to participants with opioid use disorder with no adverse effects. Nonetheless, cannabidiol may cause participants to experience side effects such as: somnolence; decreased appetite; diarrhea; transaminase elevations; fatigue, malaise, and asthenia; rash; insomnia, sleep disorder, and poor quality sleep; infections; and suicidal thoughts or actions. All participants will be told of these potential side effects, and the screening procedures, including liver function tests, are in place to minimize these potential risks. The principal investigator will continually assess and monitor adverse effects both during and after cannabidiol administration, as noted in the Schedule of Measures.

**Buprenorphine medication safety:** All subjects in this pilot trial will be stable on buprenorphine prior to enrolling, and were thus previously deemed appropriate for the medication by their buprenorphine-waived physician. Buprenorphine has been tested extensively and is FDA-approved for the treatment of OUD. Indeed, medication-assisted

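### The eligibility rule for blood and urine samples also covers Visit 3, after the last CBD dose, so as written it could remove treated subjects on a post-treatment result

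*Combined protocol and SAP*

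**What the plan says.** Section V of the protocol (Schedule of visits and assessments) gives the blood and urine samples one use. Those "collected during the Baseline Visit 1 and Post-Exposure Visit 3 will be used only for inclusion/exclusion purposes". The next sentence spells out three failures that lead to exclusion: pregnancy, liver enzymes above three times the upper limit of normal, and a toxicology failure. The last covers participants "who are not taking their buprenorphine as clinically prescribed (as confirmed by the urine toxicology) will be excluded". No visit is named in that sentence.

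The same section places dose 1 at Visit 2, after the pre-exposure assessment, and doses 2 and 3 at home. Participants then return for "Visit 3 following their last home administration of oral CBD", when the post-exposure craving assessment is made.

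Section IV puts the eligibility decision earlier: "If the subject meets the full inclusion and exclusion criteria, the subject will be enrolled".

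Section VI says the pilot is mainly meant to estimate effect sizes and variance for a larger randomized trial. It defines no analysis set and has no rule for a subject who meets an exclusion criterion after dosing. Its sample size statement is that "a sample size of 10 is needed for 88% power and two-tailed alpha set at 0.05 for a paired-samples t-test".

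On safety, section VII lists among the possible effects of CBD "somnolence; decreased appetite; diarrhea; transaminase elevations; fatigue, malaise, and asthenia", and says that "the screening procedures, including liver function tests, are in place to minimize these potential risks". It also commits the principal investigator to monitoring adverse effects during and after CBD, by reference to a schedule of measures. At the end of each session "a standardized safety and adverse events questionnaire will be used to assess any adverse events".

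**The concern.** The only use the plan gives to a Visit 3 sample is one that the sample cannot serve. By Visit 3 the subject has been enrolled and has taken the course of CBD, so there is no eligibility decision left. The one literal meaning that remains for exclusion is removal after treatment.

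That matters because removal would then depend on something measured after treatment began. Take a subject who stops buprenorphine between visits. He or she would fail the toxicology rule at Visit 3, and stopping may well be related to craving, which is the primary outcome. The remaining subjects would be those who stayed adherent. Both the mean change and its variance, which are what section VI sets out to deliver, would describe that selected group. The point holds whichever of the three tests is run at Visit 3.

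A second, conditional matter is the liver tests. If they are drawn at Visit 3, the section V wording does not connect them to the adverse-effect monitoring in section VII, although raised transaminases are a named possible effect of CBD.

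**Working it through.** **Order of events, from sections IV and V**

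1. Consent, Visit 1 samples, criteria applied, enrolment.
2. Visit 2: pre-exposure craving assessment, then dose 1.
3. Doses 2 and 3 at home.
4. Visit 3: samples and post-exposure craving assessment.

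Any result from step 4 is post-treatment. It is also obtained at the visit that completes the subject's before-and-after craving pair, so removal could discard an outcome that has been collected.

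**Reproducing the plan's power (section VI)**

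Inputs: mean change -1.5, SD 1.5, correlation 0.60, n = 10, two-sided alpha 0.05, paired t-test.

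- Taking 1.5 as the SD at each visit, SD of the change = 1.5 × √(2 × (1 − 0.60)) = 1.342.
- Standardised change = 1.5 / 1.342 = 1.118.
- Noncentral t power at n = 10: 88.1%, which matches the stated 88%.
- Taking 1.5 as the SD of the change itself gives 80.3%, which does not match. The first reading is therefore used.

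**Scale of losing treated subjects**

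The 95% CI half-width is t(0.975, n − 1) × 1.342 / √n. The numbers lost are assumed, because the documents give no rate of Visit 3 failures.

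| Subjects analysed | Power | Half-width (points) |
|---|---|---|
| 10 | 88.1% | 0.96 |
| 9 | 83.5% | 1.03 |
| 8 | 77.4% | 1.12 |

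If 1.5 were the SD of the change, the figures would be 80.3%, 74.8% and 68.1%, with half-widths of 1.07, 1.15 and 1.25.

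**Possible shift in the mean (assumed scenarios only)**

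Suppose nine retained subjects average -1.5 and one with change c is removed. The mean of all ten is (9 × (−1.5) + c) / 10.

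| c | Mean of all ten | Reported mean of nine | Overstatement |
|---|---|---|---|
| -1.5 | -1.50 | -1.50 | none |
| 0 | -1.35 | -1.50 | 1.50/1.35 = 1.11, or 11% |
| +1.5 | -1.20 | -1.50 | 1.50/1.20 = 1.25, or 25% |

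The last row is extreme: it puts the subject 3.0 points, or 3.0 / 1.342 = 2.2 SDs, from the planned mean. These rows show direction and possible size. They do not measure a bias in this trial.

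**The case against.** The best reply is that the sponsor never planned to drop treated subjects. The exclusion list in section V largely restates the enrolment criteria in section III, section VI contains no step that removes anyone, and restricting the samples to inclusion and exclusion may simply mean that they are not study outcomes. This is a fair account of probable intent. If no Visit 3 result is ever used to exclude anyone, the craving estimate is unaffected. It does not dispose of the point, because the sentence names Visit 3, the exclusion sentence that follows has no visit limit, and nothing elsewhere says what happens to a treated subject who fails.

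A second reply is that an adherence check at Visit 3 could be deliberate, since the aim concerns people in treatment and section IV says the criteria favour internal validity. That is arguable, but a post-dose exclusion would need to be prespecified in the analysis section, and it is better placed in a sensitivity analysis than in the main estimate.

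A reader might also infer that the plan forbids safety use of Visit 3 liver tests, or leaves liver effects unmonitored. The documents do not support that. The cell marks of Table 1 are not readable in the text available, so it is not known whether liver tests are drawn at Visit 3; the sentence could mean blood at one visit and urine at the other. Section VII separately commits the principal investigator to monitoring after CBD and points to a schedule for it. The drug diary, the session questionnaire and the safety meetings in section IX add to this. The liver part of the point is therefore conditional.

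**Conclusion.** The point stands as a minor defect in a stated rule. As written, section V allows a treated subject to be excluded on a post-treatment result, and section VI has nothing to prevent that from reaching the analysis.

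Its effect on the estimate is unknown and may be nil. The loss of one subject costs about 4.6 percentage points of power (88.1 − 83.5) and 0.07 points of half-width (1.03 − 0.96). These figures assume 10 analysed subjects and an SD of 1.5 at each visit. Section III enrols 12, including 2 pilot subjects, and the plan does not say whether pilot data are analysed. Power is in any case secondary here, since the stated purpose is estimation.

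It would be wrong to infer that the plan intends to discard treated subjects, or that the result is biased by 11% or 25%. No section describes such removals, and those percentages come from assumed values for one subject.

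**What to change.** In section V, limit the inclusion and exclusion use to Visit 1 samples, name the tests run at Visit 3, and state that Visit 3 results do not remove a treated subject from the craving analysis. If the sponsor wants to look at adherent subjects only, add that as a sensitivity analysis, with the main estimate kept on all treated subjects who have both assessments.

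If Table 1 schedules liver tests at Visit 3, add that the principal investigator reviews them as safety data against the same subject's Visit 1 value, under the monitoring already promised in section VII, and that they are listed descriptively. If it does not, only the wording change applies.

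The cost is a small rewording, with no new visit, sample or subject and no change to the planned paired analysis. The conditional listing has at most 12 rows. With so few subjects and no control arm, it cannot support a test or a claim that CBD caused a change.
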